5.8 Subject Withdrawal/Discontinuation Criteria

A subject's consent may be withdrawn by the subject or the subject's legally acceptable representative (as appropriate) at any time for any reason or be dropped from the trial at the discretion of the investigator should any untoward effect occur. In addition, a subject may be withdrawn by the investigator or the Sponsor if enrollment into the trial is inappropriate, the trial plan is violated, or for administrative and/or other safety reasons. Specific details regarding discontinuation or withdrawal procedures; including specific details regarding withdrawal from Future Biomedical Research, are provided in Section 7.1.4 – Other Procedures.

Discontinuation from treatment is “permanent”. Once a subject is discontinued, he/she shall not be allowed to restart treatment.

A subject must be discontinued from the trial for any of the following reasons:

- The subject or legal representative (such as a parent or legal guardian) withdraws consent/assent.

A subject must be discontinued from treatment (but may continue to be monitored in the trial) for any of the following reasons:

- The subject develops an immediate or delayed study drug-related hypersensitivity reaction.
- The subject has neutralizing ADA against MK-8962.
- The subject, in the opinion of the investigator, persistently fails to comply with dosing, evaluation or other requirements of the trial.
- Any medical condition or personal circumstance which, in the opinion of the investigator, exposes the patient to risk by continuing with the study medication or does not allow the patient to adhere to the requirements of the protocol.
- The subject develops any condition for which corifollitropin alfa, or hCG is contraindicated in accordance with the local drug label of the country where the subject is participating.
- The subject has a serious drug-related adverse event

If a subject discontinues study medication (i.e., MK-8962 and hCG obtained through the study), he should complete all Discontinuation Visit procedures as described in Section 6.0. Please refer to Section 7.1.5.3 on how to manage patients who discontinue study medication but who do not withdraw consent.

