7.2 Assessing and Recording Adverse Events

An adverse event is defined as any untoward medical occurrence in a patient or clinical investigation subject administered a pharmaceutical product and which does not necessarily have to have a causal relationship with this treatment. An adverse event can therefore be any unfavourable and unintended sign (including an abnormal laboratory finding, for example), symptom, or disease temporally associated with the use of a medicinal product or protocol-specified procedure, whether or not considered related to the medicinal product or protocol-specified procedure. Any worsening (i.e., any clinically significant adverse change in frequency and/or intensity) of a preexisting condition that is temporally associated with the use of the Sponsor's product, is also an adverse event.

Changes resulting from normal growth and development that do not vary significantly in frequency or severity from expected levels are not to be considered adverse events. Examples of this may include, but are not limited to, teething, typical crying in infants and children and onset of menses or menopause occurring at a physiologically appropriate time.

Sponsor's product includes any pharmaceutical product, biological product, device, diagnostic agent or protocol-specified procedure, whether investigational (including placebo or active comparator medication) or marketed, manufactured by, licensed by, provided by or distributed by the Sponsor for human use.

Adverse events may occur during clinical trials, or as prescribed in clinical practice, from overdose (whether accidental or intentional), from abuse and from withdrawal.

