7.2.3 Evaluating Adverse Events

An investigator who is a qualified physician will evaluate all adverse events with respect to the elements outlined in [Table 5](#). The investigator's assessment of causality is required for each adverse event. Refer to [Table 5](#) for instructions in evaluating adverse events.

Table 5 Evaluating Adverse Events

Maximum Intensity	Mild	awareness of sign or symptom, but easily tolerated (for pediatric trials, awareness of symptom, but easily tolerated)
	Moderate	discomfort enough to cause interference with usual activity (for pediatric trials, definitely acting like something is wrong)
	Severe	incapacitating with inability to work or do usual activity (for pediatric trials, extremely distressed or unable to do usual activities)
Seriousness	A serious adverse event (AE) is any adverse event occurring at any dose or during any use of Sponsor's product that:	
	† Results in death; or	
	† Is life threatening; or places the subject, in the view of the investigator, at immediate risk of death from the event as it occurred [Note: This does not include an adverse event that, had it occurred in a more severe form, might have caused death.]; or	
	† Results in a persistent or significant disability/incapacity (substantial disruption of one's ability to conduct normal life functions); or	
	† Results in or prolongs an existing inpatient hospitalization (hospitalization is defined as an inpatient admission, regardless of length of stay, even if the hospitalization is a precautionary measure for continued observation. (Note: Hospitalization for an elective procedure to treat a pre-existing condition that has not worsened is not a serious adverse event. A pre-existing condition is a clinical condition that is diagnosed prior to the use of a Merck product and is documented in the patient's medical history.); or	
	† Is a congenital anomaly/birth defect (in offspring of subject taking the product regardless of time to diagnosis); or	
	Is a cancer (although not serious per ICH definition, is reportable to the Sponsor within 24 hours to meet certain local requirements); or	
	Overdose, although not serious per ICH definition, whether accidental or intentional, with or without an accompanying adverse event/serious adverse event, is reportable to the Sponsor within 24 hours to meet certain local requirements.	

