	Other important medical events that may not result in death, not be life threatening, or not require hospitalization may be considered a serious adverse event when, based upon appropriate medical judgment, the event may jeopardize the subject and may require medical or surgical intervention to prevent one of the outcomes listed previously (designated above by a †).	
Duration	Record the start and stop dates of the adverse event. If less than 1 day, indicate the appropriate length of time and units	
Action taken	Did the adverse event cause the Sponsor's product to be discontinued?	
Relationship to Sponsor's Product	Did the Sponsor's product cause the adverse event? The determination of the likelihood that the Sponsor's product caused the adverse event will be provided by an investigator who is a qualified physician. The investigator's signed/dated initials on the source document or worksheet that supports the causality noted on the AE form, ensures that a medically qualified assessment of causality was done. This initialed document must be retained for the required regulatory time frame. The criteria below are intended as reference guidelines to assist the investigator in assessing the likelihood of a relationship between the test drug and the adverse event based upon the available information The following components are to be used to assess the relationship between the Sponsor's product and the AE; the greater the correlation with the components and their respective elements (in number and/or intensity), the more likely the Sponsor's product caused the adverse event:	
	Exposure	Is there evidence that the subject was actually exposed to the Sponsor's product such as: reliable history, acceptable compliance assessment (pill count, diary, etc.), expected pharmacologic effect, or measurement of drug/metabolite in bodily specimen?
	Time Course	Did the AE follow in a reasonable temporal sequence from administration of the Sponsor's product? Is the time of onset of the AE compatible with a drug-induced effect (applies to trials with investigational medicinal product)?
	Likely Cause	Is the AE not reasonably explained by another etiology such as underlying disease, other drug(s)/vaccine(s), or other host or environmental factors

Relationship to Sponsor's Product (continued)	The following components are to be used to assess the relationship between the Sponsor's product and the AE: (continued)	

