8.6.2 Statistical Methods for Safety Analyses

All safety analyses will be conducted for the ASaT.

Due to the small study size and single treatment, the tiered approach will not be followed for this study.

Safety and tolerability will be assessed by clinical review of all relevant parameters including AEs, laboratory tests and vital signs measurements.

For this protocol, the percentage of subjects with confirmed presence of anti-MK-8962 antibodies and its exact 95% CI will be calculated using the exact binomial method of Clopper Pearson. The presence of anti-MK-8962 antibodies will be summarized at each visit as well as overall and by treatment phase.

Adverse events (specific terms as well as system organ class terms) and predefined limits of change in laboratory and vital signs parameters will be summarized by treatment phase.

In addition, the broad AE categories consisting of the percentage of subjects with any AE, a drug related AE, a serious AE, an AE which is both drug-related and serious, and who discontinued due to an AE will be summarized by treatment phase.

Continuous measures such as changes from baseline in laboratory and vital signs parameters will be summarized: summary statistics for baseline, on-treatment, and change from baseline values will be provided by treatment phase in table format.

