9.0 LABELING, PACKAGING, STORAGE AND RETURN OF CLINICAL SUPPLIES

9.1 Investigational Product

The investigator shall take responsibility for and shall take all steps to maintain appropriate records and ensure appropriate supply, storage, handling, distribution and usage of investigational product in accordance with the protocol and any applicable laws and regulations.

Clinical Supplies will be provided by the Sponsor as summarized in [Table 8](#). This includes both MK-8962 (investigational product of this trial) and hCG (standard of care). For hCG and/or its solvent, if local regulations do not permit use of the centrally sourced supplies OR centrally sourced supplies become unavailable, a local source may be used but requires prior approval from the Sponsor.

Clinical supplies will be packaged to support enrollment and replacement subjects as required. When a replacement subject is required, the Sponsor or designee needs to be contacted prior to dosing the replacement supplies.

Table 8 Product Descriptions

Product Name & Potency	Dosage Form	Source/Additional Information
corifollitropin alfa (MK-8962) 100 µg/0.5 mL	Pre-filled syringe (Sterile Solution for subcutaneous Injection, 0.5 mL)	Provided centrally by the Sponsor.
corifollitropin alfa (MK-8962) 150 µg/0.5 mL	Pre-filled syringe (Sterile Solution for subcutaneous Injection, 0.5 mL)	
human Chorionic Gonadotropin (hCG) 1500 IU	Ampoule or vial (Sterile Dry Powder for subcutaneous injection after reconstitution)	Provided centrally by the Sponsor. If local regulations do not permit use of the centrally sourced supplies OR centrally sourced supplies become unavailable, a local source may be used but requires prior approval from the Sponsor.
human Chorionic Gonadotropin (hCG) 5000 IU	Ampoule or vial (Sterile Dry Powder for subcutaneous injection after reconstitution)	
Sodium Chloride Solution 0.9%, 1 mL	Ampoule or vial (Sterile Solution for Reconstitution of hCG, 1 mL)	

All supplies indicated in [Table 8](#) will be provided per the “Source/Additional Information” column depending on local country operational requirements.

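### In the 52-week combined phase, the single causality answer per adverse event cannot separate MK-8962 from hCG, and the status of locally sourced hCG is undefined

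*Combined protocol and SAP*

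**What the plan says.** Section 7.2.3 states that "The investigator's assessment of causality is required for each adverse event". Table 5 in that section puts the question as "Did the Sponsor's product cause the adverse event", and the answer is one of two options, yes or no. No separate answer per drug is described. The same table, introducing its guidance, speaks instead of "assessing the likelihood of a relationship between the test drug and the adverse event based upon the available information".

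Section 7.2 defines the term broadly: "Sponsor's product includes any pharmaceutical product, biological product, device, diagnostic agent or protocol-specified procedure", whether investigational or marketed, if it is "manufactured by, licensed by, provided by or distributed by the Sponsor for human use". Section 9.1 and Table 8 show that the Sponsor supplies both MK-8962 and hCG. Section 9.1 adds that, where local rules bar the central hCG supply or it becomes unavailable, "a local source may be used but requires prior approval from the Sponsor".

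Two places use the resulting label. Section 8.6.2 summarises, by treatment phase, the percentages of subjects with any AE and with "a drug related AE, a serious AE, an AE which is both drug-related and serious", without saying which drug is meant. Section 5.8 lists among the reasons for stopping treatment: "The subject has a serious drug-related adverse event". The second primary objective in Section 3.1 is the safety and tolerability of MK-8962.

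**The concern.** The safety objective names one drug, but the causality label covers two for most of the treatment period. The trial is uncontrolled, so there is no hCG-only arm against which to compare event rates. Investigator attribution is then the main event-level means of telling the two drugs apart, and the form of the question removes it.

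The overlap is foreseeable. The notes on hCG dosing in Sections 5.2 and 5.2.1.2 name gynecomastia and breast pain or tenderness as grounds for considering hCG doses outside the stated range. Such an event, attributed by the investigator to Sponsor-provided hCG, would enter the same drug-related percentage as a reaction attributed to MK-8962.

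At stake are the two drug-related rows in Section 8.6.2, the reading of the Section 5.8 criterion, and the Section 7.2.2.1 duty to report related serious events that come to light outside the regular reporting window.

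**Working it through.** The documents give no figure to reproduce; this is a check of definitions, with simple arithmetic for its extent.

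**Step 1: does the term cover both drugs?** The definition in Section 7.2 is met if the Sponsor makes, licenses, provides or distributes the product. Section 9.1 has the Sponsor providing MK-8962 and, by default, hCG. Both are inside the term. A yes in Table 5 is therefore consistent with MK-8962, hCG or both as the cause, and also with a protocol-specified procedure.

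**Step 2: do the supporting items in Table 5 separate the drugs?** The dechallenge item asks whether the Sponsor's product was stopped or reduced. Under Section 5.2.1.2 hCG is titrated, while under Section 5.2.1.1 a subject on MK-8962 150 µg is not down-titrated. A positive dechallenge need not concern MK-8962.

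**Step 3: how much of the treatment period is affected?** Inputs: 12 weeks of MK-8962 alone and 52 weeks combined (Section 1.0); MK-8962 every 14 days from Day 1 to Day 435 (Section 6.0); first hCG dose on Day 85 (Table 2).

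- Combined phase: 52/64 = 81.25% of scheduled weeks.
- Priming phase: 12/64 = 18.75%.
- MK-8962 doses: (435 − 1)/14 + 1 = 32.
- Doses before Day 85 (Days 1, 15, 29, 43, 57, 71): 6. Doses from Day 85 on: 32 − 6 = 26, and 26/32 = 81.25%.

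Because Section 8.6.2 reports by phase, hCG is absent from the priming-phase rows. Separation from hCG is thus available for about 19% of scheduled treatment and not for the other 81%.

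**Step 4: sensitivity of the percentages.** With about 15 subjects, moving one subject in or out of a category changes a percentage by 1/15 = 6.7 points. This would be true of any reclassification and does not say how often this one would occur.

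**Step 5: locally sourced hCG.** It is Sponsor's product if the Sponsor makes, licenses, provides or distributes it. The documents do not state its maker or licensee, or whether a locally sourced product counts as provided by the Sponsor. If none of the conditions applies, Table 5 treats it as another drug, hence an alternative cause, and directs a no where another cause is more likely. If one applies, the answer for the same event would be yes. The documents do not settle which.

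**The case against.** The strongest reply is that the combination is what is being studied. Section 8.1 describes the design as investigating MK-8962 in combination with hCG, so attribution to the regimen is defensible, and in a single-arm trial per-drug attribution rests on judgement alone. This stands as a reason to keep a related-to-either row. It does not show that the combined answer can serve an objective worded for MK-8962.

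The effect on safety conclusions is also limited. Between allocation and follow-up, adverse events, serious events and events of clinical interest are reported regardless of relatedness (Sections 7.2 to 7.2.2.2). The pre-specified safety endpoint is anti-MK-8962 antibodies, and the hypersensitivity event of interest is tied to the MK-8962 injection. No test is attached to the drug-related rows. All of this stands.

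The AE form and the data entry guidelines are not among the documents, and may already hold a field per product. That also stands; if so, Table 5 and Section 8.6.2 should say so.

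Three stronger readings are tempting but not supported:

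- A reader might infer that the drug-related rows never isolate MK-8962 from hCG. The priming-phase summary does, since no hCG is given then.
- A reader might infer that locally sourced hCG is excluded, so that the label differs between sites. Exclusion depends on facts the documents do not give. Local supply is an exception needing approval, and nothing shows that any site will use it. Section 5.8 describes study medication as MK-8962 and hCG obtained through the study, without distinguishing supply routes.
- A reader might turn 81% of treatment time into most adverse events. That assumes a roughly constant event rate, which the documents do not provide.

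**Conclusion.** The point holds for the combined phase. As written, one causality answer covers MK-8962 and Sponsor-provided hCG for 52 of 64 weeks, so the drug-related and drug-related-and-serious percentages for that phase cannot address the safety of MK-8962 as distinct from hCG. This conclusion rests on Table 5 as printed and assumes that the AE form adds no per-drug field.

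The status of locally sourced hCG is an unresolved definition. Differing codes by supply route are a possible consequence if such hCG is used and falls outside the term; they are not an established defect.

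The consequence is a loss of interpretability in a few descriptive rows, plus ambiguous wording in Section 5.8. The events themselves and the antibody endpoint are not compromised. It is worth correcting because the correction is cheap and the trial has no comparator to supply the missing information.

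**What to change.** 1. In Table 5 and on the AE form, unless the form already does this, ask two questions for each event: relationship to MK-8962, and relationship to hCG whatever its source. Allow yes to both, and mark the hCG question not applicable before the first hCG dose.
2. In Section 8.6.2, report by phase the subjects with MK-8962-related, hCG-related and related-to-either adverse events, and likewise for serious events. A subject with an event judged related to both counts in each single-drug row and once in the either row.
3. Ask the sponsor to reconcile the wording of drug-related, test drug and Sponsor's product across Sections 5.8, 7.2 (with Table 5), 8.6.2 and 9.1, and to state whether locally sourced hCG is covered. The scope of the discontinuation criterion in Section 5.8 is for the sponsor to settle; this point does not propose one.

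The cost is one more field per adverse event, a short amendment to Table 5 and Section 8.6.2, and a few more table rows. The downside is that, with two drugs given together, some attributions will be both or uncertain. The related-to-either row keeps those events visible.

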7.2.2 Immediate Reporting of Adverse Events to the Sponsor

7.2.2.1 Serious Adverse Events

A serious adverse event is any adverse event occurring at any dose or during any use of Sponsor's product that:

- Results in death;
- Is life threatening;
- Results in persistent or significant disability/incapacity;
- Results in or prolongs an existing inpatient hospitalization;
- Is a congenital anomaly/birth defect;
- Is an other important medical event.

Note: In addition to the above criteria, adverse events meeting either of the below criteria, although not serious per ICH definition, are reportable to the Sponsor in the same timeframe as SAEs to meet certain local requirements.

- Is a cancer;
- Is associated with an overdose.

Refer to [Table 5](#) for additional details regarding each of the above criteria.

For the time period beginning when the consent form is signed until treatment allocation/randomization, any serious adverse event, or follow up to a serious adverse event, including death due to any cause, that occurs to any subject must be reported within 24 hours to the Sponsor if it causes the subject to be excluded from the trial, or is the result of a protocol-specified intervention, including but not limited to washout or discontinuation of usual therapy, diet, placebo treatment or a procedure.

For the time period beginning at treatment allocation/randomization through the follow-up visits following cessation of treatment, any serious adverse event, or follow up to a serious adverse event, including death due to any cause, whether or not related to the Sponsor's product, must be reported within 24 hours to the Sponsor either by electronic media or paper. Electronic reporting procedures can be found in the EDC data entry guidelines. Paper reporting procedures can be found in the Investigator Trial File Binder (or equivalent).

Additionally, any serious adverse event, considered by an investigator who is a qualified physician to be related to the Sponsor's product that is brought to the attention of the investigator at any time outside of the time period specified in the previous paragraph also must be reported immediately to the Sponsor.

All subjects with serious adverse events must be followed up for outcome.

7.2.2.2 Events of Clinical Interest

Selected non-serious and serious adverse events are also known as Events of Clinical Interest (ECI) and must be reported to the Sponsor.

For the time period beginning when the consent form is signed until treatment allocation/randomization, any ECI, or follow up to an ECI, that occurs to any subject must be reported within 24 hours to the Sponsor if it causes the subject to be excluded from the trial, or is the result of a protocol-specified intervention, including but not limited to washout or discontinuation of usual therapy, diet, placebo treatment or a procedure.

For the time period beginning at treatment allocation/randomization through the follow-up visits following cessation of treatment, any ECI, or follow up to an ECI, whether or not related to the Sponsor's product, must be reported within 24 hours to the Sponsor, either by electronic media or paper. Electronic reporting procedures can be found in the EDC data entry guidelines. Paper reporting procedures can be found in the Investigator Trial File Binder (or equivalent).

Events of clinical interest for this trial include:

1. an elevated AST or ALT lab value that is greater than or equal to 3X the upper limit of normal and an elevated total bilirubin lab value that is greater than or equal to 2X the upper limit of normal and, at the same time, an alkaline phosphatase lab value that is less than 2X the upper limit of normal, as determined by way of protocol-specified laboratory testing or unscheduled laboratory testing.*

*Note: These criteria are based upon available regulatory guidance documents. The purpose of the criteria is to specify a threshold of abnormal hepatic tests that may require an additional evaluation for an underlying etiology. The trial site guidance for assessment and follow up of these criteria can be found in the Investigator Trial File Binder (or equivalent).

2. Hypersensitivity reaction: A potential sign or symptom of a hypersensitivity reaction after injection of MK-8962 such as new emergent skin rash, urticaria, hypotension, allergic asthma, chest tightness, broncho-spasm, dyspnea, or wheezing. Minor localized skin rash not suggesting hypersensitivity will not be considered an ECI.

